## **8. STATISTICAL SOFTWARE**

All data listings, summaries, and statistical analyses will be generated using SAS® version 9.4 or later.

**9. CHANGES TO PROTOCOL SPECIFIED ANALYSES**

ECG variables at each visit will not be analyzed in this study.

**APPENDIX A. SMQ CATEGORIES ADVERSE EVENTS AND ADVERSE EVENTS OF INTEREST**Depression (excl suicide and self injury) (SMQ) – narrow search

Activation syndrome  
Adjustment disorder with depressed mood  
Adjustment disorder with mixed anxiety and depressed mood  
Agitated depression  
Anhedonia  
Antidepressant therapy  
Childhood depression  
Decreased interest  
Depressed mood  
Depression  
Depression postoperative  
Depressive symptom  
Dysphoria  
Electroconvulsive therapy  
Feeling guilty  
Feeling of despair  
Feelings of worthlessness  
Helplessness  
Major depression  
Menopausal depression  
Post stroke depression  
Postictal depression  
Postpartum depression

Suicide/self-injury (SMQ) – narrow search

Completed suicide  
Depression suicidal  
Intentional overdose  
Intentional self-injury  
Poisoning deliberate  
Self-injurious behaviour  
Self-injurious ideation  
Suicidal behaviour  
Suicidal ideation  
Suicide attempt

Akathisia (SMQ) – narrow and broad search

Akathisia  
Extrapyramidal disorder  
Hyperkinesia  
Hyperkinesia neonatal  
Motor dysfunction

Movement disorder  
Psychomotor hyperactivity  
Restlessness

Parkinson-like events (SMQ) – narrow and broad search

Action tremor  
Akinesia  
Bradykinesia  
Bradyphrenia  
Cogwheel rigidity  
Drooling  
Dysphonia  
Extrapyramidal disorder  
Freezing phenomenon  
Gait disturbance  
Hypertonia  
Hypertonia neonatal  
Hypokinesia  
Hypokinesia neonatal  
Masked facies  
Micrographia  
Mobility decreased  
Motor dysfunction  
Movement disorder  
Muscle rigidity  
Muscle tone disorder  
Musculoskeletal stiffness  
On and off phenomenon  
Parkinson's disease  
Parkinson's disease psychosis  
Parkinsonian crisis  
Parkinsonian gait  
Parkinsonism rest tremor  
Parkinsonism  
Parkinsonism hyperpyrexia syndrome  
Postural reflex impairment  
Postural tremor  
Resting tremor  
Tremor  
Tremor neonatal  
Walking disability

Somnolence and sedation – preferred terms

Sedation  
Somnolence  
Sopor  
Stupor

Lethargy

Torsade de pointes/QT prolongation (SMQ) – narrow and broad search

Cardiac arrest  
Cardiac death  
Cardiac fibrillation  
Cardio-respiratory arrest  
Electrocardiogram QT interval abnormal  
Electrocardiogram QT prolonged  
Electrocardiogram U-wave abnormality  
Electrocardiogram repolarization abnormality  
Long QT syndrome  
Long QT syndrome congenital  
Loss of consciousness  
Sudden cardiac death  
Sudden death  
Syncope  
Torsade de pointes  
Ventricular arrhythmia  
Ventricular fibrillation  
Ventricular flutter  
Ventricular tachyarrhythmia  
Ventricular tachycardia

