**6.9.7. 12-lead Electrocardiogram**

All ECGs will be performed after at least 5 minutes rest in a supine or semi-recumbent position. 12-lead ECGs to assess safety will be collected according to the [Schedule of Events](#). Heart rate and ECG intervals (PR, QRS, QT, and QTcF) and clinical interpretation will be assessed by the central reader.

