#### **8.4. Safety Endpoints**

The following safety endpoints will be assessed in Part A:

- Incidence of adverse events, serious adverse events, severe adverse events, drug-related adverse events, adverse events leading to withdrawal during the following periods:
  - Overall
  - During titration
  - During long-term treatment
- Observed values and changes from baseline in clinical laboratory parameters (hematology, chemistry, and urinalysis)
- Observed values and changes from baseline in vital signs
- Observed values in ECG parameters and abnormal findings
- Number of subjects with on-treatment QTcF values >450 ms, >480 ms, >500 ms, or a change from Baseline in QTcF of >30 ms or >60 ms
- Observed values and changes in UPDRS Part III (motor examination), BARS, HADS, C-SSRS, ESS, and MoCA©
- Duration of time to achieve stable dosing of SD-809

The following secondary safety endpoints will be assessed in Part B:

- Incidence of adverse events, serious adverse events, severe adverse events, drug-related adverse events, and adverse events leading to withdrawal
- Observed values and changes from start of randomized withdrawal in clinical laboratory parameters (hematology, chemistry, and urinalysis)
- Observed values and changes from start of randomized withdrawal in vital signs
- Observed values in ECG parameters and abnormal findings
- Number of subjects with on-treatment QTcF values >450 ms, >480 ms, >500 ms, or a change from Baseline in QTcF of >30 ms or >60 ms
- Observed values and changes in UPDRS Part III (motor examination), BARS, HADS, C-SSRS, ESS, and MoCA©

The following secondary safety endpoints will be assessed in Part C:

- Secondary safety endpoints:
  - Incidence of adverse events, serious adverse events, severe adverse events, drug-related adverse events, and adverse events leading to withdrawal from start of Part C
  - Observed values and changes in vital signs from start of Part C
  - Observed values and changes in C-SSRS from start of Part C
  - Observed values in ECG parameters and abnormal findings from start of Part C

- Number of subjects with on-treatment QTcF values >450 ms, >480 ms, >500 ms, or a change from Baseline in QTcF of >30 ms or >60 ms from start of Part C

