## 2.2. Primary and Secondary Measures and Endpoints

### 2.2.1. Safety Measures and Endpoints

The safety measures and endpoints in Part A are as follows:

1. Incidence of AEs, SAEs, severe AEs, drug related AEs, AEs leading to withdrawal, AEs leading to dose reduction, AEs leading to dose suspension during the following periods: overall, during titration, and during long-term treatment
2. Observed values and changes from baseline in clinical laboratory parameters (hematology, chemistry, and urinalysis)
3. Observed values and changes from baseline in vital signs
4. Observed values in electrocardiogram (ECG) parameters and abnormal findings
5. Number of patients with on-treatment QTcF (Fridericia-corrected QT interval) values >450 ms, >480 ms, >500 ms, or a change from baseline in QTcF of >30 ms or >60 ms.
6. Observed values and changes in Unified Parkinson's Disease Rating Scale (UPDRS) Part III (motor examination), Barnes Akathisia Rating Scale (BARS), Hospital Anxiety and Depression Scale (HADS), Columbia-Suicide Severity Rating Scale (C-SSRS), Epworth Sleepiness Scale (ESS), and MoCA® (Montreal Cognitive Assessment)

The safety measures and endpoints in Part B (Randomized Withdrawal Period) are as follows:

1. Incidence of adverse events, serious adverse events, drug-related adverse events, and adverse events leading to withdrawal.
2. Observed values and changes from start of randomized withdrawal in clinical laboratory parameters (hematology, chemistry, and urinalysis)
3. Observed values and changes from start of randomized withdrawal in vital signs
4. Observed values in electrocardiogram (ECG) parameters and abnormal findings
5. Number of patients with on-treatment QTcF (Fridericia-corrected QT interval) values >450 ms, >480 ms, >500 ms, or a change from baseline in QTcF of >30 ms or >60 ms.
6. Observed values and changes in UPDRS Part III (motor examination), BARS, HADS, C-SSRS, ESS, and MoCA®

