#### **7.1.7. Electrocardiogram**

Shifts (normal, abnormal not clinically significant, and abnormal clinically significant) from baseline of this study to each Part A visit that this is measured will be summarized using patient counts.

The number of patients with postbaseline QTcF values >450 ms, >480 ms, >500 ms, or a change from baseline in QTcF of >30 ms or >60 ms, PR interval values >200 ms, QRS duration values >100 ms, and QT interval values >500 ms will be summarized using descriptive statistics. This summary will be repeated for patients who have a normal QTcF at baseline according to the protocol definition.

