#### **7.2.6. Electrocardiogram**

Shifts (normal, abnormal not clinically significant, and abnormal clinically significant) from the Pre-Withdrawal Visit to each Part B visit that this is measured will be summarized using patient counts.

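### Observed ECG values are a listed safety endpoint in Parts A and B, but SAP Section 9 drops their by-visit analysis, so neither the size and time course of a mean QTcF shift nor the randomised Part B QTcF contrast is summarised

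*SAP*

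**What the plan says.** **Endpoints.** SAP 2.2.1 lists, as item 4 for Part A and again for Part B, "Observed values in electrocardiogram (ECG) parameters and abnormal findings". Protocol 8.4 has the same endpoint: "Observed values in ECG parameters and abnormal findings". Item 5, also given for both Parts, is the "Number of patients with on-treatment QTcF (Fridericia-corrected QT interval) values >450 ms, >480 ms, >500 ms", together with changes above 30 and 60 ms. Protocol 8.3 says that ECG parameters will be summarised.

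**The change.** SAP Section 9 consists of one sentence: "ECG variables at each visit will not be analyzed in this study". It gives no reason and names no substitute.

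**What is left in Part A (SAP 7.1.7).** There are tables of "Shifts (normal, abnormal not clinically significant, and abnormal clinically significant) from baseline of this study to each Part A visit", and "The number of patients with postbaseline QTcF values >450 ms, >480 ms, >500 ms" with QTcF change above 30 or 60 ms and cut-offs for PR, QRS and QT. The threshold counts are not by visit. SAP 7.1.3 adds the Torsade de pointes/QT prolongation query, with Kaplan-Meier curves and exposure-adjusted rates by time period.

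**What is left in Part B (SAP 7.2.6).** "Shifts (normal, abnormal not clinically significant, and abnormal clinically significant) from the Pre-Withdrawal Visit to each Part B visit", and nothing else.

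**The data.** Protocol 6.9.7: "Heart rate and ECG intervals (PR, QRS, QT, and QTcF) and clinical interpretation will be assessed by the central reader".

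**The concern.** QT prolongation is a monitored risk in this study. The protocol has a QTcF discontinuation criterion (5.2.5), extra ECGs after a change of antipsychotic (6.7.1) and a list of prohibited or restricted QT-prolonging drugs (Appendix 14). The intervals are measured numerically at Baseline, after at least a week off study drug, and repeatedly afterwards. For laboratory tests, vital signs and most rating scales the SAP plans by-visit values and changes. For ECG intervals it plans no mean, SD or change anywhere.

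Two results would be missing from the report: how far QTcF moves on average during long-term treatment and when, and how it differs between patients kept on SD-809 and patients switched to placebo in the randomised week. The second is the study's only concurrently controlled look at QTcF. An endpoint that the SAP still lists would also have part of its content unreported.

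**Working it through.** The plan states no figure for this point. The check sets each endpoint against its analysis, then illustrates what the retained counts can show.

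**1. Endpoint against analysis**

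| SAP 2.2.1 endpoint | Part A (7.1.7) | Part B (7.2.6) |
|---|---|---|
| Item 4, abnormal findings | shift table by visit | shift table by visit |
| Item 4, observed values | any-time threshold counts; no numeric summary | none |
| Item 5, QTcF thresholds | any-time counts | none |

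SAP 7.1.1 presents Part A safety summaries for both Parts combined unless noted otherwise, so Part B ECGs may enter the 7.1.7 counts. Those tables are grouped by parent-study treatment, however, and so do not compare the randomised arms.

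Read literally, Section 9 also conflicts with the by-visit shift tables in 7.1.7 and 7.2.6, and with the ECG column of the visit windows in SAP 4.5 (Weeks 2, 4, 6, 28, 41, 54, 106 and 158).

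**2. What the threshold counts can show**

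Inputs: 330 patients (Protocol synopsis, planned Part A size); QTcF change normal with mean m and SD s; one post-baseline value each. The documents give no SD, so 10 to 20 ms is assumed.

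Expected number above cut-off c = 330 × [1 − Φ((c − m)/s)].

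| s (ms) | >30 ms, m = 0 | >30 ms, m = 5 | >30 ms, m = 10 | >60 ms, m = 10 |
|---|---|---|---|---|
| 10 | 0.4 | 2.0 | 7.5 | 0.0 |
| 15 | 7.5 | 15.8 | 30.1 | 0.1 |
| 20 | 22.0 | 34.9 | 52.4 | 2.0 |

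Example: s = 15, m = 10 gives 330 × [1 − Φ(20/15)] = 330 × 0.0912 = 30.1.

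The >30 ms count responds to a shift, but it cannot identify one: 7.5 patients fits a 10 ms shift at SD 10 and no shift at SD 15.

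**3. Effect of the number of ECGs**

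SAP 7.1.7 counts a patient if any post-baseline value exceeds the cut-off. With k ECGs per patient and correlation ρ between a patient's changes, the probability is 1 − ∫ φ(z) Φ((30 − m − s√ρ z)/(s√(1 − ρ)))^k dz. For k = 8 (the scheduled Part A visits), s = 15, m = 0 and an assumed ρ = 0.5, this gives about 38 of 330 with no shift at all (about 29 at ρ = 0.7 and 46 at ρ = 0.3). That is more than the 30 expected from a true 10 ms shift with one ECG each. Follow-up differs between patients, so the count mixes shift, variability and number of ECGs, and it has no time axis.

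**4. What restored summaries would give**

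Half-width of the 95% interval for a mean change at one visit = 1.96 s/√n, with n assumed:
- n = 250: 1.96 × 15/15.81 = 1.9 ms; 1.96 × 20/15.81 = 2.5 ms.
- n = 100: 1.96 × 15/10 = 2.9 ms; 1.96 × 20/10 = 3.9 ms.

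Part B difference between arms, with 143 randomised (SAP 2.3), or about 71.5 per arm: 1.96 s√(2/71.5) = 4.9 ms at SD 15 and 6.6 ms at SD 20.

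**The case against.** The strongest defence is that the SAP declares the change in the section meant for such changes. Its introduction says that the SAP prevails and that differences from the protocol will be explained in the clinical study report. Protocol 8.3 names only laboratory and vital-sign parameters for change from baseline; for ECG it asks for a normal/abnormal classification, which the SAP delivers. A change-from-baseline table for intervals therefore goes beyond the protocol. That last part stands. But Protocol 8.3 and 8.4 do ask for observed ECG values to be summarised. SAP 2.2.1 still lists them, and a later explanation does not supply the missing result.

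A reader might go further and infer that a QTcF shift could not be seen at all, that Section 9 removes the endpoint's only analysis, or that threshold counts barely move with a modest shift. The documents do not support these readings. Part A keeps shift tables by visit, counts on observed QTcF, PR, QRS and QT values, QTcF change counts, and the Torsade/QT query with rates by period. The >60 ms count does stay near zero, but the >30 ms count rises roughly 2.4-fold (SD 20) to 4-fold (SD 15) with a 10 ms shift. Large individual prolongations would appear.

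It is also fair to say that a Part A mean change would be uncontrolled. Patients meeting the QTcF discontinuation criterion leave, psychoactive medication may change after three months (Protocol 6.11.1), and ECG timing relative to dose is set only for visits after an antipsychotic change. Late-visit means would be descriptive. None of this applies with the same force to the one-week randomised comparison in Part B.

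**Conclusion.** The point holds as a gap between listed endpoints and planned output. In Part A, the numeric part of item 4 is reduced to any-time threshold counts. In Part B, it has no summary, and item 5 has none by randomised arm. What is lost is the size and time course of the mean QTcF shift and the study's only randomised QTcF contrast; detection of large individual prolongations is not lost.

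The mismatch rests on the text alone. The illustration rests on an assumed SD of QTcF change (10 to 20 ms), normality, an assumed within-patient correlation and assumed visit numbers. Those assumptions set the size of the counts and half-widths. They do not alter the conclusion that one any-time count cannot separate a shift from greater variability or more ECGs. No risk to patients during the study follows from this, because central reading and the discontinuation criterion are unaffected.

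**What to change.** 1. Delete the sentence in SAP Section 9. If some ECG output is still to be dropped, name it and give the reason, so that it no longer conflicts with the shift tables and visit windows.
2. In SAP 7.1.7, add descriptive statistics for observed values and change from Baseline of this study in QTcF, PR and QRS at each scheduled ECG visit, with a 95% interval for the mean QTcF change. Resting heart rate is already covered under vital signs.
3. In SAP 7.2.6, add the same from the Pre-Withdrawal Visit by randomised arm, and add the item 5 QTcF threshold counts by arm.
4. Label the Part A means as descriptive, uncontrolled and affected by dropout at late visits.

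The cost is a few table shells and some SAP wording. No new data are needed, because the intervals are already collected and read centrally.
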